#### *2.4.4.1.5 Sensitivity to the use of calculated versus measured LDL-C measurements*

In order to assess the robustness of the primary analysis to the use of calculated versus measured LDL-C assessments, an ANCOVA model will be run using measured LDL-C within Week 24 analysis window. This model will include the treatment group, the baseline value for measured LDL-C and the randomization strata. Patients from ITT population with a measured LDL-C at baseline and at least 1 measured LDL-C available within Week 24 analysis window will be included in the analysis.

#### *2.4.4.1.6 Subgroup analyses*

To assess the homogeneity of the treatment effect across various subgroups, treatment-by-subgroup factor, time point-by-subgroup factor and treatment-by time point-by subgroup factor interaction terms and a subgroup factor term will be added in the primary MMRM model. LS mean difference versus ezetimibe at Week 24 will be provided, as well as the corresponding SE and 95% CI, within each subgroup. The significance level of the treatment-by-subgroup factor interaction term at Week 24 will also be provided for each factor for descriptive purpose. Forest plots will be provided. In order to handle unbalances between randomization stratification factors levels, population weights will be used as for the primary analysis model.

Subgroups of interest are:

- BMI (<30 kg/m^2, ≥30 kg/m^2);
- Gender (Female, Male);
- Age (<65 years, ≥65 to <75 years, ≥75 years);
- High intensity statin treatment (atorvastatin 40 to 80 mg daily or rosuvastatin 20 to 40 mg daily versus atorvastatin below 40 mg daily, rosuvastatin below 20 mg daily or simvastatin whatever the daily dose);
- Prior history of myocardial infarction (MI) or ischemic stroke (Yes, No);
- Diabetes (Yes, No);
- Moderate CKD (Yes, No);

- Baseline LDL-C (<2.59,  $\geq$ 2.59 to <3.37,  $\geq$ 3.37 to <4.14,  $\geq$ 4.14 mmol/L): for this specific subgroup factor, the MMRM model will include fixed categorical effects for treatment group, randomization strata (as per IVRS), baseline LDL-C category, time point, and the interactions treatment-by-time point, strata-by-time point, baseline LDL-C category-by-time point, treatment group-by-baseline LDL-C category, and treatment group-by-baseline LDL-C category-by-time point;
- Baseline HDL-C (<1.04 mmol/L,  $\geq$ 1.04 mmol/L);
- Baseline fasting TG (<1.70 mmol/L,  $\geq$ 1.70 mmol/L, ie, mixed dyslipidemia);
- Baseline Lp(a) (<0.3,  $\geq$ 0.3 to <0.5,  $\geq$ 0.5 g/L);

If the subgroup factor is a randomization stratification factor, then the IVRS strata will be used.

#### **2.4.4.2 Analyses of secondary efficacy endpoints**

##### *2.4.4.2.1 Continuous endpoints anticipated to have a normal distribution*

Continuous secondary variables defined in [Section 2.1.3.2](#) anticipated to have a normal distribution (ie, lipids other than TG and Lp[a]) will be analyzed using the same MMRM model as for the primary endpoint with fixed categorical effects of treatment group, randomization strata (as per IVRS), planned time points up to Week 24, treatment-by-time point interaction and strata-by-time point interaction, as well as, the continuous fixed covariates of corresponding baseline value and baseline value-by-time point interaction.

##### *2.4.4.2.2 Continuous endpoints anticipated to have a non-normal distribution*

Continuous secondary efficacy variables defined in [Section 2.1.3.2](#) anticipated to have a non-normal distribution (ie, TG and Lp[a]) will be analyzed using multiple imputation approach for handling of missing values. The percent change from baseline at time point of interest will be derived from observed and imputed lipid values at this time point. Multiple imputation will be followed by robust regression model (3) with endpoint of interest as response variable using M-estimation (using SAS ROBUSTREG procedure) with treatment group, randomization strata (as per IVRS, as defined in [Section 1.1](#)) and corresponding baseline value(s) as effects to compare treatment effects. Combined means estimates for both treatment groups, as well as the differences of these estimates, with their corresponding SEs, 95% CIs and p-value will be provided through the SAS MIANALYZE procedure. In case the number of patients is lower than 10 in a given stratum (eg, MI/Ischemic Stroke = Yes), the corresponding stratum (eg, MI/Ischemic Stroke) term will be removed from the multiple imputation and robust regression models.

##### *Multiple imputation model*

Since in general the missing pattern is anticipated not to be monotone, a two-step approach will be used:

- Step 1: The Markov Chain Monte Carlo (MCMC) method will be used in conjunction with the IMPUTE = MONOTONE option to create an imputed data set with a monotone missing pattern;

- Step 2: Using the monotone data set from step 1, missing data will be imputed using the regression method.

The imputation model for step 1 will include the treatment group and the values of the analyzed parameter at baseline and time-points up to Week 24.

The imputation model for step 2 will include the same variables as in step 1 with the following additional variables:

- The randomization strata;
- Age, BMI, and gender (age and BMI included as continuous variables).

Data will be log-transformed before imputation process and then back-transformed to create the imputed data sets using the TRANSFORM statement of SAS MI procedure.

#### 2.4.4.2.3 *Binary endpoints*

Binary secondary efficacy endpoints defined in [Section 2.1.3.2](#) will be analyzed using multiple imputation approach for handling of missing values as described for non-normally distributed endpoints but without log-transformation (see [Section 2.4.4.2.2](#) for details about multiple imputation).

For each simulation leading to negative imputed value, another value will be redrawn using MINIMUM option of MI SAS procedure.

The binary endpoint at time point of interest will be derived from observed and imputed lipid values at this time point. Multiple imputation will be followed by stratified logistic regression with treatment group as main effect and corresponding baseline value(s) as covariate, stratified by randomization factors (as per IVRS, as defined in [Section 1.1](#)). Combined estimates of odds ratio versus ezetimibe, 95% CI, and p-value will be obtained through the SAS MIANALYZE procedure.

In case the number of patients is lower than 10 in a given stratum (eg, MI/Ischemic Stroke = Yes), the corresponding stratum (eg, MI/Ischemic Stroke) term will be removed from the multiple imputation and logistic regression models.

In the data dependent case when such logistic regression is not applicable (eg, the response rate is zero in one treatment arm and thus the maximum likelihood estimate may not exist), the last observation carried forward (LOCF) approach would be used for handling of missing values and a stratified exact conditional logistic regression would be performed to compare treatment effects. The LOCF imputation method will consist of using the last value obtained up to the Week 24 analysis window (Week 12 respectively) to impute the missing Week 24 value (Week 12 respectively).

In case of computing issues with exact logistic regression, the baseline level(s) will be entered in the model as a categorical variable(s) using quartiles. In case the model would not converge with

stratification variables, an unstratified exact logistic regression will be performed. Exact odds ratio versus ezetimibe, 95% CI, and p-value will be provided.

#### ***2.4.4.2.4 Sensitivity analyses of key secondary endpoints***

In order to assess secondary endpoints during the efficacy treatment period, the same statistical approach as described above from [Section 2.4.4.2.1](#) to [Section 2.4.4.2.3](#) will be applied during the efficacy treatment period in the mITT population (see [Section 2.3.1.2](#)).

#### ***2.4.4.2.5 Analyses of key secondary endpoints by subgroups***

The endpoint “the percent change in fasting TG from baseline to Week 24” will be analyzed according to the following subgroups:

- Baseline fasting TG (<150 mg/dL [ $<1.70 \text{ mmol/L}$ ],  $\geq 150 \text{ mg/dL} [\geq 1.70 \text{ mmol/L}]$  ie, mixed dyslipidemia).

#### ***2.4.4.2.6 Summary of results per time point***

Central laboratory values, percent change from baseline, and/or when appropriate absolute change from baseline, for calculated LDL-C, TC, HDL-C, fasting TG, non HDL-C, and T C/HDL-C ratio at Week 4, Week 8, Week 12, Week 16, Week 24 time points, for Lp(a), Apo B, Apo A-1 at Week 12 and Week 24 time points will be summarized in the ITT population using:

- For lipids other than TG and Lp(a): LS mean and SE for each treatment group, obtained from the same MMRM models as used for endpoints above including planned time points and with raw values, changes from baseline, or percent change from baseline as response variable in the model as appropriate.
- For TG and Lp(a): mean and SE for each treatment group obtained from multiple imputation approach followed by the robust regression models as used for endpoints above including planned time points and with raw values or percent changes from baseline as response variable in the model as appropriate.

In addition, quantitative descriptive summaries by time point (value at visit and % change from baseline) will be presented for all lipids using observed (ie, non-missing) data. In addition binary variables for LDL-C will be also described by time point.

#### ***2.4.4.3 Multiplicity issues***

In order to handle multiple key efficacy secondary endpoints, the overall type-I error will be controlled by the use of a sequential inferential approach. Statistical significance of the primary parameter at the 0.05 alpha level is required before drawing inferential conclusions about first key secondary parameter (refer to the order in [Section 2.1.3.2.1](#)). Inferential conclusions about successive key secondary parameters require statistical significance at the 0.05 alpha level of the prior ones.

This fixed hierarchical approach will ensure a strong control of the overall type-I error rate at the 0.05 level.

No further adjustments will be made for other secondary efficacy endpoints for which p-values will be provided for descriptive purpose only.

#### **2.4.4.4 Additional efficacy analysis(es)**

Not applicable.

#### **2.4.5 Analyses of safety data**

The summary of safety results will be presented by treatment group. No formal inferential testing will be performed. Summaries will be descriptive in nature.

##### ***General common rules***

All safety analyses will be performed on the safety population as defined in [Section 2.3.2](#), unless otherwise specified, using the following common rules:

- Safety data in patients who do not belong to the safety population (eg, exposed but not randomized) will be listed separately;
- The baseline value is defined as the last available value obtained up to the date and time of the first double-blind IMP administration (capsule or injection, whichever comes first), except otherwise specified.
- The potentially clinical significant abnormality (PCSA) values are defined as abnormal values considered medically important by the Sponsor according to predefined criteria/thresholds based on literature review and defined by the Sponsor for clinical laboratory tests and vital signs (PCSA version dated January 2009 [[Appendix A](#)]). In case the threshold defined in the PCSA list for a given lab parameter is below the ULN, the following PCSA criterion will be used for the PCSA analysis: >PCSA threshold or > ULN (if  $ULN \geq PCSA$  threshold).
- PCSA criteria will determine which patients had at least 1 PCSA during the TEAE period, taking into account all evaluations performed during TEAE period, including nonscheduled or repeated evaluations.
- The treatment-emergent PCSA denominator by group for a given parameter will be based on the number of patients assessed for that given parameter at least once during the TEAE period.

All measurements, scheduled or unscheduled, fasting or not fasting, will be assigned to analysis windows defined in [Section 2.5.4, Table 2](#) in order to provide an assessment for Week 4 to Week 24 time points.

- For quantitative safety parameters based on central laboratory/reading measurements, descriptive statistics will be used to summarize results and change from baseline values by visit and treatment group using analysis windows. Summaries will also include the last on-treatment value and the worst on-treatment value. The last on-treatment value is defined as the last value collected during the treatment period (see [Section 2.1.4](#)). The worst on-

treatment value is defined as the nadir and /or the peak value during the treatment period according to the direction (minimum or maximum) of the abnormality as defined in the PCSA list.

- For exploratory purpose, key safety analyses could also be provided according to up-titration status, ie, according to whether the patients remained on the 75 mg dose or whether they were up-titrated to 150 mg. These analyses will be exploratory and descriptive (no formal comparison per dose) as it is expected that there could be inherent differences in the baseline characteristics between those patients titrating to 150 mg and those remaining on 75 mg. In order to reduce the bias of this analysis, the period before the up-titration time point (planned at Week 12) will be analyzed separately since only the dose 75 mg is proposed for this time period and consequently the early events occurring before Week 12 can only be attributed to this dose. Therefore the descriptive analysis per dose will include any safety events occurring from the first injection post Week 12 IVRS/IWRS transaction to the end of the TEAE period. Baseline characteristics of patients receiving each dose will be summarized.

Analyses performed according to diabetes status will be done considering diabetic patients as patients with either type 1 or type 2 diabetes in the medical history e-CRF page (regardless of the ongoing status).

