10.4.3 General guidelines for reporting adverse events

All AEs regardless of seriousness or relationship to IMP, spanning from the signature of the ICF, until the end of the study (post-study treatment follow up visit), are to be recorded on the corresponding screen(s) included in the e-CRF.

Whenever possible, diagnosis or single syndrome should be reported instead of symptoms. The Investigator should specify the date of onset, intensity, action taken with respect to IMP, corrective treatment/therapy given, additional investigations performed, outcome and his/her opinion as to whether there is a reasonable possibility that the AE was caused by the IMP.

Laboratory, vital signs or ECG abnormalities are to be recorded as AEs only if:

- Symptomatic and/or
- Requiring either corrective treatment or consultation, and/or
- Leading to IMP discontinuation or modification of dosing, and/or
- Fulfilling a seriousness criterion, and/or
- Defined as an AE of special interest with immediate notification.

See [Appendix C](#) for a summary of AE reporting guidelines.

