### ***Other baseline characteristics***

Other baseline characteristics include body mass index (BMI) in kg/m^2 (quantitative and qualitative variables: <30, ≥30), smoking status, alcohol habits and randomization strata (as defined in [Section 1.1](#)) as per IVRS and e-CRF.

Statin treatment stratum as per e-CRF will be derived using the statin name and dose taken the day of the randomization. If a patient takes neither atorvastatin, rosuvastatin nor simvastatin the day of randomization, stratum will be equal to the low/moderate dose stratum defined as “simvastatin whatever the dose, atorvastatin below 40 mg daily or rosuvastatin below 20 mg daily”. In case of combination of statins, stratum will be allocated to the high dose stratum defined as “atorvastatin 40 to 80 mg daily or rosuvastatin 20 to 40 mg daily” if at least one of the statins taken is in this category. If a patient takes atorvastatin, rosuvastatin or simvastatin the day of randomization but the daily dose is missing from the e-CRF, the stratification applied at randomization (ie, IVRS strata) will be applied.

Glycated hemoglobin A1c (HbA1c) (quantitative and qualitative variable: <5.7%, ≥5.7% to <6.5%, ≥6.5%), and efficacy lipid parameters (quantitative variables for all efficacy parameters and the following qualitative variables) will be also summarized at baseline (definitions in [Section 2.1.3](#)):

- calculated LDL-C: <1.81, ≥1.81 to <2.59, ≥2.59 to <3.37, ≥3.37 to <4.14, ≥4.14 to <4.91, ≥4.91 mmol/L;
- HDL-C: <1.04, ≥1.04 mmol/L;
- Fasting TG: <1.7, ≥1.7 to <2.3, ≥2.3 mmol/L, category ≥1.7mmol/L (mixed dyslipidaemia) will be also displayed;
- Lp(a): <0.3, ≥0.3 to <0.5, ≥0.5 g/L, category ≥0.3g/L will be also displayed.

Any technical details related to computation, dates, and imputation for missing dates is described in [Section 2.5](#).

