### **2.1.5 *Other endpoints***

The assessment endpoint listed below is defined using the same definitions and rules as for calculated LDL-C, when applicable (see [Section 2.1.3.1](#)).

- The absolute change in HbA1c (%) from baseline to Week 12 and Week 24. PCSA criteria for HbA1c will be used (see [Appendix A](#)).
- The proportion of patients with 2 consecutive results, spaced out by at least 21 days, of calculated LDL-C <25 mg/dL (<0.65 mmol/L) (respectively calculated LDL-C <15 mg/dL, ie, <0.39 mmol/L) during the treatment period and the time to the first calculated LDL-C <25 mg/dL (respectively, calculated LDL-C <15 mg/dL for these patients).

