### ***Analysis of all treatment-emergent adverse events***

The following treatment-emergent adverse event summaries will be generated for the safety population.

- Overview of TEAEs, summarizing number (%) of patients with any
  - TEAE;
  - Serious TEAE;
  - TEAE leading to death;
  - TEAE leading to permanent treatment discontinuation;
- All TEAEs by primary SOC, HLGT, HLT, and PT, showing number (%) of patients with at least 1 TEAE sorted by the SOC internationally agreed order. The other levels (HLGT, HLT, PT) will be presented in alphabetical order;
- All TEAEs by primary SOC and PT, showing the number (%) of patients with at least 1 TEAE, sorted by the internationally agreed SOC order and by decreasing incidence of PTs within each SOC. This sorting order will be applied to all other tables, unless otherwise specified;
- All TEAEs by treatment group regardless of relationship in one column and, in the same table a second column with TEAEs related to alirocumab according to investigator's opinion by primary SOC, HLGT, HLT, and PT, sorted by the sorting order defined above;
- All TEAEs by maximal intensity (ie, mild, moderate, or severe), presented by primary SOC and PT, sorted by the sorting order defined above;
- Kaplan-Meier curves will be provided, when appropriate, for time from first dose of double-blind IMP (capsule or injection, whichever comes first) to the first occurrence of selected TEAEs. Patients without any event will be censored at the end of the TEAE period. Selected TEAEs could be local injection site reactions, general allergic reactions, hepatic disorders, diabetes among non-diabetic patients at baseline and TEAE related to any clinically significant signal that needs further characterization.

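### Baseline diabetes status for the safety analyses ignores baseline HbA1c, and the only HbA1c cut-off applied after baseline is above 8%

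*SAP*

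**What the plan says.** **Status.** SAP 2.4.5, General common rules, defines diabetes status for safety analyses by "considering diabetic patients as patients with either type 1 or type 2 diabetes in the medical history e-CRF page", whether or not the condition is ongoing. No laboratory criterion enters.

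**Baseline HbA1c.** For baseline values, "The baseline value is defined as the last available value obtained up to the date and time of the first double-blind IMP administration". The protocol flow chart schedules HbA1c at Week -3, Week 12 and Week 24 (and at follow-up only after an abnormal end-of-treatment value), so baseline HbA1c is normally the screening result. SAP 2.1.1 describes it as "Glycated hemoglobin A1c (HbA1c) (quantitative and qualitative variable: <5.7%, ≥5.7% to <6.5%, ≥6.5" percent, but only as a baseline characteristic.

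**HbA1c after baseline.** SAP 2.1.5 gives absolute change to Weeks 12 and 24 and adds that "PCSA criteria for HbA1c will be used". Appendix A sets that criterion at above 8%. SAP 2.4.6 adds summary statistics by visit and PCSA incidence, each also by baseline diabetes status.

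**Diabetes events.** SAP 2.4.5.1 tabulates the diabetes adverse-event grouping overall and by baseline status. It also names, among possible Kaplan-Meier analyses, "diabetes among non-diabetic patients at baseline and TEAE related to any clinically significant signal".

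**From laboratory value to adverse event.** Protocol 10.4.3: "Laboratory, vital signs or ECG abnormalities are to be recorded as AEs only if" they are symptomatic, need treatment or consultation, change IMP dosing or lead to its discontinuation, are serious, or are an AESI with immediate notification.

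**The concern.** The by-status tables are meant to separate worsening of known diabetes from diabetes appearing on treatment. That separation is only as good as the baseline classification, and the classification sets aside a result that every patient should have. If undiagnosed patients sit in the non-diabetic stratum, a diagnosis first recorded on treatment is read as new when the laboratory evidence preceded the first dose.

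The second half concerns what is counted afterwards. A cut-off of 8% lies well above the SAP's own top baseline boundary of 6.5%. Patients in the non-diabetic stratum who move from below 6.5% to between 6.5% and 8% are the ones a diabetes safety review would want to see, and no HbA1c table counts them. Such patients are plausible here: protocol 7.1 lists impaired glucose tolerance or impaired fasting glucose as an acceptable reason for a lower statin dose.

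**Working it through.** The plan states no figure on this point, so there is none to reproduce. The check traces two example patients through the rules and then illustrates the size.

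**Patient A: no diabetes entry, screening HbA1c 7.5%.**
- Exclusion E18 covers diabetes diagnosed within 3 months before Week 0 and poorly controlled diabetes with HbA1c above 9% at screening. Without a diagnosis, neither applies, so the patient can be randomised.
- SAP 2.4.5 classes the patient non-diabetic; SAP 2.1.1 places the same patient in the top HbA1c category. The two are not linked.
- A first diabetes report after the first dose enters the non-diabetic rows of the by-status adverse-event table and, if it is produced, the Kaplan-Meier curve.

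**Patient B: no diabetes entry, HbA1c 6.0% at screening and 7.0% on treatment.**
- HbA1c PCSA (above 8%): not counted.
- Normal-range table in SAP 2.4.5.3: reserved for parameters without a PCSA, so HbA1c is not covered.
- Adverse event: only if a protocol 10.4.3 condition is met.
- Glucose PCSA (fasting, 7 mmol/L or more; SAP 2.4.5.3 and Appendix A): counted by status, but only if glucose also crosses its threshold.
- HbA1c summaries in SAP 2.4.6: the value contributes to the mean, median, range and absolute change. The crossing is not counted.

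**How many patients could be misplaced.** Let s be the share with recorded diabetes and u the share of the rest with baseline HbA1c of 6.5% or more. The documents give neither. Assume s = 30% to 70% and u = 2% to 10%; arm sizes are the planned 400 and 200.

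Misplaced = arm size × (1 − s) × u
- Alirocumab: 400 × 0.30 × 0.02 = 2.4, up to 400 × 0.70 × 0.10 = 28
- Ezetimibe: 200 × 0.30 × 0.02 = 1.2, up to 200 × 0.70 × 0.10 = 14

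**Effect on the comparison.** Let p be the true incident risk (assumed 2% alirocumab, 1% ezetimibe, ratio 2.0) and d the probability that a misplaced patient is first reported on study (assumed 25% to 100%).

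Observed risk = (1 − u) × p + u × d

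| u | d | Alirocumab | Ezetimibe | Ratio | Difference (points) |
|---|---|---|---|---|---|
| 2% | 25% | 0.98 × 2% + 0.5% = 2.46% | 0.98 × 1% + 0.5% = 1.48% | 1.66 | 0.98 |
| 5% | 50% | 0.95 × 2% + 2.5% = 4.40% | 0.95 × 1% + 2.5% = 3.45% | 1.28 | 0.95 |
| 10% | 100% | 0.90 × 2% + 10% = 11.80% | 0.90 × 1% + 10% = 10.90% | 1.08 | 0.90 |

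The term u × d is the same in both arms because randomisation balances u in expectation and blinding gives no reason for d to differ. The ratio therefore moves towards 1, while the difference shrinks only by the factor 1 − u.

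**The case against.** Several points limit the concern, and most of them stand.

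- **Other routes exist.** A reader might infer that a rise across 6.5% goes unrecorded altogether. The documents do not support that. A rise that is treated or referred becomes an adverse event. The diabetes grouping (SAP 2.1.4.1) includes the carbohydrate-tolerance investigation terms apart from the two decreases, and fasting glucose of 7 mmol/L or more is counted by status. The gap is an HbA1c-based count of rises that nobody acted on.
- **The HbA1c data are not uninformative.** A reader might infer that they could neither show nor exclude progression to diabetes. Yet SAP 2.4.6 reports HbA1c by visit, arm and diabetes status, so a shift between arms in the non-diabetic stratum would be visible. The number of patients behind it would not.
- **The contamination route is narrow.** Investigators see the screening HbA1c, and protocol section 10 makes them responsible for optimising treatment when it is high. A diagnosis made before Week 0 triggers E18, and adverse events before the first dose are reported separately. Patient A arises only where the result leads to no diagnosis until treatment has begun.
- **Prevalent cases need not outnumber incident ones.** That inference compares misplaced patients with events. A misplaced patient becomes an event only if first reported on study, and the documents give no rate for this.
- **6.5% is not a diagnosis here.** The SAP uses it as a descriptive category; neither document defines diabetes by a single HbA1c value.
- **No formal endpoint is affected.** The Kaplan-Meier curve is optional, and no inferential testing of safety data is planned.

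None of this explains why a baseline value already collected and categorised is left out of baseline status, or why the same categories are not carried forward.

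**Conclusion.** The concern holds as a minor gap in the descriptive safety analysis. Two statements follow directly from the text: diabetes status rests on history alone, so a patient with no history and a screening HbA1c of 6.5% to 9% can be classed non-diabetic; and the only HbA1c cut-off after baseline is above 8%, so no HbA1c table counts movement from below 6.5% into the range 6.5% to 8%.

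The size is unknown. The ranges calculated above rest wholly on assumed values of s, u, d and the incident risks, and show direction rather than an expected result. Misplaced patients dilute a ratio and favour neither arm systematically; the risk difference is little changed. The primary and key secondary analyses are untouched.

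**What to change.** **SAP 2.4.5.** For the diabetes adverse-event, glucose and HbA1c analyses by status, class a patient as non-diabetic when there is no diabetes history and baseline HbA1c is below 6.5%. Keep the history-only version as a supportive display for comparability with earlier studies. Name the outputs to which the new definition applies, so that the diabetes subgroup of the primary endpoint (SAP 2.4.4.1.6) is not altered by accident.

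**SAP 2.4.6.** Add a shift table by arm from the SAP 2.1.1 HbA1c categories at baseline to the same categories at Weeks 12 and 24, with the number of baseline non-diabetic patients reaching 6.5% or more. Leave the PCSA of above 8% unchanged.

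**Cost.** Some SAP wording before database lock, one extra table, the retained supportive display and a slightly smaller non-diabetic stratum. All the HbA1c values needed are already scheduled.
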